markers, such as CRP, in the presence of unrelated inflammatory stimuli, such as concurrent infections and systemic diseases (16,17). For instance, in other diseases like meningitis, blood IL-6 is less specific than IL-6 in the drainage fluid (18). In addition, abdominal drainage fluid is more effective and efficient than routinely collected blood for detecting anastomotic leakage (AL) following colorectal cancer surgery. However, fewer studies have been conducted to predict the recovery of postoperative gastrointestinal function by analyzing drainage fluid. We believe that analyzing postoperative gastrointestinal drainage fluid is of greater clinical importance in predicting postoperative gastrointestinal function.

In our study, we collected abdominal drainage fluid near the anastomosis on the first and third day after laparoscopic colorectal cancer surgery for biochemical and cytological tests. These tests included lactate dehydrogenase (LDH), adenosine deaminase (ADA) and albumin. We also performed conventional cytological tests for neutrophils, lymphocytes, monocytes, etc. In addition, we calculated inflammatory indices such as neutrophil-lymphocyte ratio (NLR), lymphocyte-monocyte ratio (LMR) and prognostic nutrition index (PNI). We also collected peripheral blood for the same cytological indices and evaluated the outcome of the patients' gastrointestinal function recovery using the I-FEED score. In addition, we analyzed the correlation between the above indices and PODG, and combined the inflammation indices of peritoneal drainage and serum to predict the outcome of gastrointestinal function recovery after laparoscopic colorectal cancer surgery, aiming to improve the accuracy and effectiveness of prediction and accelerate patient recovery.

2. Purpose of the study

Primary purpose: The study aims to examine the role of markers lactate dehydrogenase (LDH), neutrophil-lymphocyte ratio (NLR) as markers of inflammation, in the prediction of postoperative gastrointestinal dysfunction (POGD) in drainage fluids on day 1 following laparoscopic colorectal cancer surgery.

Secondary objective: 1. The study aims to examine the role of markers lactate dehydrogenase (LDH), neutrophil-lymphocyte ratio (NLR) as markers of inflammation, in the

prediction of POGD in drainage fluids on day 3 following laparoscopic colorectal cancer surgery.

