2. The study aims to explore the correlation between albumin, adenosine deaminase (ADA), lymphocyte-monocyte ratio (LMR), prognostic nutritional index (PNI) and other inflammation indicators in drainage fluids on day 1 and day 3 following colorectal cancer surgery, and the occurrence of POGD.

3. The study aims to explore the correlation between neutrophil-lymphocyte ratio (NLR), lymphocyte-monocyte ratio (LMR), platelet-lymphocyte ratio (PLR), systemic immune-inflammatory index (SII), and other inflammation indicators in peripheral blood on day 1 and day 3 following colorectal cancer surgery, and the occurrence of POGD.

4. Combined inflammatory markers in peritoneal fluid and peripheral blood to predict POGD.

5. To evaluate the practical application of the I-FEED score in clinical practice.

3. Study endpoints

Primary endpoint:

Grading of postoperative gastrointestinal function (according to the scoring system based on intake, sensation of nausea, vomiting, physical examination, and duration of symptoms (I-FEED). normal (0-2), postoperative gastrointestinal intolerance (POGI) (3-5), and postoperative gastrointestinal dysfunction (POGD) (>6).

Secondary endpoints:

- a. Time to first postoperative deflation.
- b. Time to first postoperative bowel movement.
- c. Time to first postoperative food tolerance.
- d. Morbidity and mortality from 30-day postoperative complications .

4. Outcome Measures

Primary Outcome Measure:

Measurement of drainage fluid lactate dehydrogenase (LDH) and neutrophil to lymphocyte ratio (NLR) on postoperative day 1

Secondary Outcome Measure :

- a. Measurement of drainage fluid LDH and neutrophil to lymphocyte ratio (NLR) on postoperative day 3.
- b. Measurement of drainage fluid albumin, adenosine deaminase (ADA), lymphocyte-monocyte ratio (LMR), prognostic nutritional index (PNI) on postoperative day 1.
- c. Measurement of drainage fluid albumin, adenosine deaminase (ADA), lymphocyte-monocyte ratio (LMR), prognostic nutritional index (PNI) on postoperative day 3
- d. Measurement of blood serum neutrophil-lymphocyte ratio (NLR), lymphocyte-monocyte ratio (LMR), platelet-lymphocyte ratio (PLR), systemic immune-inflammatory index (SII) on postoperative day 1.
- e. Measurement of blood serum neutrophil-lymphocyte ratio (NLR), lymphocyte-monocyte ratio (LMR), platelet-lymphocyte ratio (PLR), systemic immune-inflammatory index (SII) on postoperative day 3.

4.Sample collection

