Patient drainage fluid was collected on the first and third postoperative days. All samples were transferred to the laboratory for analysis within 30 minutes, and collected samples were aliquoted into 2 ml cryotubes and stored at -80 degrees Celsius until further use. Cytological analyses for neutrophils, lymphocytes, monocytes, etc. were performed using a Sysmex XN 1500 (Sysmex, Shanghai). Biochemical assays were performed using an AU480 chemistry analyzer (Beckman Coulter, USA) with enzyme kinetic assay for lactate dehydrogenase, peroxidase assay for adenosine deaminase and bromocresol green assay for albumin.

5.Follow-up plan

Content	Cytology (drainage fluid)	Biochemical (drainage fluid)	Biochemistry (peripheral blood)	Cytology (peripheral blood)	Consultation	medical examination	pathological results
preoperative			√	√			√
POD.1	√	√		√	√	√	
POD.2					√	√	
POD.3	√	√		√	√	√	
POD.4					√	√	
POD.5					√	√	
postoperative							√

POD: Post-operative day

6. Study Design

Study Type: Prospective single-central observational study

Observational Study Model: Case-Only

Study Start: February 18, 2024

Estimated completion date: October 1, 2024

7. Study population

7.1 Inclusion Criteria:

- Preoperative diagnosis of colorectal cancer through colonoscopy biopsy.
- Patients aged 18-80 years.
- Underwent laparoscopic radical resection for colorectal cancer with confirmed postoperative pathology.
- No prior radiotherapy, chemotherapy, or immunotherapy before surgery.
- Voluntary participation in the study and signing of a written informed consent form.

7.2 Exclusion Criteria:

- Pregnant or lactating women.
- Severe liver dysfunction (Child-Pugh class B or above); severe renal dysfunction

(serum creatinine level greater than 177).

- Patients with severe heart failure, chronic obstructive pulmonary disease, and other underlying diseases.
- Patients with pre-existing severe infections (developing sepsis or not improving after antibiotic treatment) before surgery.
- Patients with postoperative fistulas or those requiring a two-stage anastomosis.
- Intraoperative and postoperative intraperitoneal chemotherapy.
- Blood disorders (leukemia, lymphoma, aplastic anemia, etc.).
- Patient or family member withdraws midway;
- Intraoperative or postoperative instability of vital signs requires admission to the intensive care unit.
- Those with serious post-operative infections (e.g., incisional, lung, and urinary tract infections)

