## 4. Sample size calculation

In a previously published study conducted at our institution, the incidence of postoperative prolonged ileal obstruction (PPOI) was approximately 38.0% (1), a figure we approximated to be equivalent to the incidence of postoperative gastric dysfunction (POGD). The ratio of the POGD group to the non-POGD group was approximately 3:5. Sample sizes were determined based on the primary study endpoints, and the mean lactate dehydrogenase (LDH) in the POGD group on postoperative day 1 (POD.1) was  $(1406.5 \pm 70)$ , as per the pretest results. The mean LDH for the non-POGD group was  $1210 \pm 343$ . Utilizing a one-sided, two-sample unequal-variance t-test with a power of 0.8 and an  $\alpha$ -value of 0.05, calculated using PASS2021 (NCSS, USA), the required number of cases was determined to be 45. The Neutrophil-to-Lymphocyte Ratio (NLR) value for the POD.1 POGD group was  $(156.3 \pm 14.7)$ , while the mean NLR value for the non-POGD group was  $(39.4 \pm 37.5)$ . The calculated sample size for this comparison was 8 cases, with a maximum sample size of 45 cases. In this study, age and TNM stage were primarily controlled as confounders. Assuming that 5 event samples are required to control for each variable, an additional sample of 14 cases is necessary,

bringing the total required sample size to 59 cases. Considering a 5% dropout rate, the final recruitment requirement is 63 cases.

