## **5. Statistical analysis**

Statistical analyses were performed by SPSS statistical software v.17.0 (SPSS Inc., Chicago, IL, USA) and R Language v.4.0.3 (R Foundation for Statistical Computing, Vienna, Austria). Measures that met normality were expressed as mean  $\pm$  standard deviation were analyzed using the t-test, and measures that did not meet normality were expressed as median and interquartile range and analyzed using the Mann-Whitney rank sum test. The cutoff value was selected by the use of the Youden index (sensitivity + specificity - 1), and the count data were expressed as number of cases and percentages and analyzed using chi-square test. Predictors of postoperative complications and POGD were studied by univariate and multivariate logistic regression (LR). The diagnostic performance of biomarkers was assessed by receiver operator curve (ROC) analysis.

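### Preoperative blood counts are collected, but the plan names no use for them when it relates POD1 and POD3 blood indices to POGD (secondary objective 3)

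*Protocol*

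**What the plan says.** - **Eligibility.** Protocol section 7.2 excludes "Patients with pre-existing severe infections (developing sepsis or not improving after antibiotic treatment) before surgery". It also excludes "Patients with severe heart failure, chronic obstructive pulmonary disease, and other underlying diseases", without defining the last group, and blood disorders. Section 7.1 rules out earlier radiotherapy, chemotherapy or immunotherapy.
- **Data collected.** The protocol's follow-up plan (section 5) ticks peripheral blood cytology in the preoperative, POD1 and POD3 rows.
- **Objectives.** Secondary objective 3 (protocol section 2) relates NLR, LMR, PLR, SII "and other inflammation indicators in peripheral blood on day 1 and day 3 following colorectal cancer surgery, and the occurrence of POGD". Outcome measures d and e name the same four indices on POD1 and on POD3. Secondary objective 4 reads "Combined inflammatory markers in peritoneal fluid and peripheral blood to predict POGD" and gives no time point.
- **Analysis.** SAP section 4 states: "In this study, age and TNM stage were primarily controlled as confounders". SAP section 5 lists group comparisons, univariate and multivariate logistic regression, ROC analysis and a Youden cutoff. It gives no covariate list and mentions neither a preoperative value nor a change from one.
- **Background.** Protocol section 1 argues that drain fluid is less prone than other sources to raised inflammatory markers "in the presence of unrelated inflammatory stimuli, such as concurrent infections and systemic diseases".

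**The concern.** A blood NLR on POD1 or POD3 contains the patient's level before surgery as well as the response to surgery. If the preoperative level also bears on POGD, a raw postoperative index can be associated with POGD even where the surgical response is not. The protocol's own background recognises that unrelated inflammation moves inflammatory markers, and the schedule already collects the measurement that could account for part of it. The institution's earlier study, which SAP section 4 cites for the 38% incidence, is described in its title as predicting prolonged ileus from age and inflammatory markers. The title does not say when those markers were measured, so it shows only that such confounding is plausible.

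At stake is how a positive result for objective 3 is read: as a sign of postoperative inflammation, or as something a count taken before surgery would have shown already.

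**Working it through.** **1. Is the preoperative value available, and is it used?** The schedule column that supplies the POD1 and POD3 blood indices is also ticked before surgery, so I take it that the same indices can be computed preoperatively. Objective 3 and outcome measures d and e name days 1 and 3 only; objective 4 names no day; SAP section 4 names age and TNM stage; SAP section 5 names no covariate. No objective or analysis mentions the preoperative count.

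**2. What could the preoperative level do?** The documents give no correlation between preoperative and postoperative values, so ρ = 0.3, 0.5 and 0.7 are assumptions. Let X be the log preoperative index and Y the log postoperative index, with equal SDs (also an assumption).

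- Shared variance: ρ².
- If only X drives POGD, with slope β per SD, Y analysed alone shows a slope of about ρβ (linear approximation). With X in the model, the expected slope of Y is zero.
- Price of adjustment: the standard error of the Y slope grows by about 1/√(1−ρ²) (linear approximation).
- For the log ratio Y−X: its SD relative to that of Y is √(2(1−ρ)), and its correlation with X is −√((1−ρ)/2).

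| ρ | Shared variance | Spurious slope of Y alone | SE factor if adjusted | Relative SD of log ratio | Correlation of log ratio with X |
|---|---|---|---|---|---|
| 0.3 | 9% | 0.3β | 1.05 | 1.18 | −0.59 |
| 0.5 | 25% | 0.5β | 1.15 | 1.00 | −0.50 |
| 0.7 | 49% | 0.7β | 1.40 | 0.77 | −0.39 |

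β is unknown, so the confounding itself cannot be sized. The log ratio stays correlated with X at every ρ shown, because it fixes the preoperative slope at 1. It therefore need not remove confounding, and below ρ = 0.5 it is noisier than the raw value.

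A further figure, 1 − √(1−ρ²), gives reductions in residual SD of 5%, 13% and 29%. It applies only where the marker is the outcome, as in the group comparison, and the preoperative level is unrelated to POGD. It does not describe a gain in the logistic model.

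**3. Is there room in the model?** The plan's own figures first: 5 events per variable at 38% incidence gives 5/0.38 = 13.2, so 14 cases; 45 + 14 = 59; 59/0.95 = 62.1, so 63. These match SAP section 4. (The 14 cases cover one variable although two are named; that is a separate matter.) Expected events at 59 cases: 59 × 0.38 = 22.4.

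| Model | Terms | Events per term |
|---|---|---|
| Age, TNM (one term), postoperative index | 3 | 22.4/3 = 7.5 |
| The same plus preoperative index | 4 | 22.4/4 = 5.6 |
| Objective 4 example: age, TNM, drain LDH, drain NLR, one blood index | 5 | 22.4/5 = 4.5 |
| Objective 4 example plus preoperative index | 6 | 22.4/6 = 3.7 |

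Four terms at 5 events each need 20 events, that is 20/0.38 = 52.6, so 53 cases, which 59 covers. This rests on the 38% incidence: 20 events in 59 cases needs 20/59 = 34%. At 30%, the top of the range that protocol section 1 gives for ileus, there would be 17.7 events, or 4.4 per term.

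**The case against.** The strongest reply is that nothing in the documents says objectives 3 and 4 are meant to isolate the response to surgery. Objective 3 explores a correlation, objective 4 predicts, and SAP section 5 assesses diagnostic performance. For prediction, a raw POD1 or POD3 value is a legitimate predictor whatever its source. This stands. A reader might infer that the raw analyses are invalid; the documents do not support that. What remains is the interpretation of an association, and whether the postoperative index says more than the preoperative one.

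Second, SAP section 4 says that age and TNM stage were controlled primarily, and SAP section 5 lists no covariates. A reader might infer that the preoperative counts are excluded from every analysis. In fact their use is unspecified, not ruled out. It still needs prespecifying.

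Third, adjustment has a price. If the total postoperative level, and not the change, drives POGD, the extra term only widens the interval, by the factors shown. With about 22 events this matters, and it is why the adjusted result should stand beside the unadjusted one and not replace it.

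**Conclusion.** The point holds for secondary objective 3, as an improvement that should be made and not as a flaw that undermines the study. The plan collects a preoperative value of each blood index and names no use for it, so an association between a POD1 or POD3 blood index and POGD may partly reflect the level before surgery. How large that part is cannot be derived from the documents; the figures above rest on assumed correlations and equal SDs.

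Three stronger readings are tempting and are not supported:

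- **That the eligibility rule is at fault, or that inflamed patients certainly enter.** The infection criterion leaves milder or treated infection eligible, but the undefined group of other underlying diseases may remove some such patients. The text supports only that they may enter, and the matter can be handled in the analysis.
- **That the primary objective is affected.** It concerns drain-fluid LDH and NLR on POD1, which have no preoperative counterpart.
- **That a comparison of drain fluid with blood is distorted.** No objective or SAP section specifies a head-to-head comparison, and adjusting blood alone would make one asymmetric.

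**What to change.** In SAP section 5:

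- Keep the raw POD1 and POD3 analyses, the ROC analysis and the cutoffs as planned.
- For objective 3, add one prespecified logistic model for POGD per blood index (NLR, LMR, PLR, SII) and day. Each contains the postoperative index, the log preoperative value of the same index, age and TNM stage, and is reported beside the unadjusted result.
- Do not use the log ratio of postoperative to preoperative value as a substitute, for the reasons in the check above.
- Do not add the preoperative term to the objective 4 combined model where events per term would fall below the plan's own 5. The five-term example above is already at 4.5.

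Cost: no new samples and no change to eligibility; some SAP wording and eight further models (four indices, two days). Each uses one extra term, which takes events per term from 7.5 to 5.6 with TNM stage as one term. With TNM stage as two terms it would be 4.5, and fewer than 20 events would also bring it below 5; the report should say so if either happens. Raising recruitment is not needed for the 5-events rule at 38% incidence. If the sponsor instead followed its own practice of adding 14 cases per variable, 59 would become 73, and 73/0.95 = 76.8, so 77 recruited.

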- Intraoperative conversion to open laparotomy.

8. Peri-operative procedures

The surgery was performed by an experienced surgeon (deputy head physician or above). The patient fasted for 6 hours and prohibited drinking water for 2 hours before the operation. General anesthesia was administered using static aspiration combined with endotracheal intubation under predominantly long-acting intravenous opioids (e.g. sufentanil). Anastomosis was performed using routine linear or circular techniques for resection of the left half of the colon, right half of the colon, sigmoid colon, and rectum, without the routine use of manual suture reinforcement. Drains were routinely placed in the post-operative period and removed after approximately 3 days post-operatively, once anastomotic fistulae and peritoneal effusion were excluded. Post-operative analgesia was provided. The patient utilized a patient-controlled intravenous paroxysmal pain regimen consisting of sufentanil (0.2ug/kg), tolstanesetron (5mg), and dizocin (20mg). Within 48 hours after surgery, the patient is allowed to consume fluids and enteral nutrition is gradually resumed as tolerated by the

patient. Patients were encouraged to mobilize early and were assisted in getting out of bed as they desired.

9. Ethics Statement

The study was conducted in accordance with the Declaration of Helsinki (as revised in 2013). The study was approved by the Ethics Committee of Chaoyang Central Hospital of China Medical University (2024 No. 02). Each subject was informed and signed an informed consent form prior to enrolment.

10. Reference

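### Fistula, serious infection and ICU admission after surgery are exclusions with no time window, so the events that endpoint (d) should count are removed and the day-1 prediction set can depend on later events

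*Protocol*

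**What the plan says.** Three of the criteria in Protocol section 7.2 refer to events after surgery:

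- On infection: "Those with serious post-operative infections (e.g., incisional, lung, and urinary tract infections"
- On fistula: "Patients with postoperative fistulas or those requiring a two-stage anastomosis"
- On ICU admission: "Intraoperative or postoperative instability of vital signs requires admission to the intensive care unit"

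None has a time limit, and serious is explained only by examples. Part of the ICU criterion is intraoperative and so precedes any sample; this point concerns the postoperative part.

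The primary purpose in Protocol section 2 is "prediction of postoperative gastrointestinal dysfunction (POGD) in drainage fluids on day 1 following laparoscopic colorectal cancer surgery". Secondary objective 1 repeats this for day 3. Secondary endpoint (d) in Protocol section 3 is "Morbidity and mortality from 30-day postoperative complications". SAP section 5 plans logistic regression for predictors of both postoperative complications and POGD, with ROC analysis and a Youden cutoff for the biomarkers.

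On timing, Protocol section 8 says only that drains are "removed after approximately 3 days post-operatively, once anastomotic fistulae and peritoneal effusion were excluded". In the text available, neither document defines an analysis set or says what happens to a sampled patient who later meets one of these criteria.

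**The concern.** Two things are at stake.

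**Endpoint (d) and the complication model.** Fistula, serious infection and ICU admission are themselves complications within 30 days. Excluding patients who have them removes the more serious part of what endpoint (d) is meant to count, along with any death that follows. Milder complications remain, so the SAP model would describe predictors of those alone.

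**Day-1 prediction.** A clinician reading drain LDH or NLR on day 1 does not know who will later leak, become infected or go to intensive care. If such patients are taken out afterwards, the reported accuracy belongs to a group defined by hindsight. For leaks the removal may also be related to the marker, because Protocol section 1 states that "abdominal drainage fluid is more effective and efficient than routinely collected blood for detecting anastomotic leakage (AL) following colorectal cancer surgery".

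**Working it through.** **1. Do the passages conflict?** Section 7.2 removes patients with the three events at any time after surgery. Section 3 counts complications to 30 days, and SAP section 5 models them. The same event cannot be both a reason for removal and a counted outcome, and no stated rule resolves this.

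**2. Can removal follow the day-1 sample?** Nothing limits the criteria to events before it. For fistula, the drain-removal rule in section 8 has fistula ruled out at about day 3, so status can be settled after day 1. That is an inference. No passage times infection or ICU admission.

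**3. Size of the effect on endpoint (d).** SAP section 4 ends: "bringing the total required sample size to 59 cases. Considering a 5% dropout rate, the final recruitment requirement is 63 cases". The last step reproduces: 59/0.95 = 62.1, rounded up to 63. Take N = 63 as the operated patients. The documents give no complication rate, so the following counts are assumptions: s patients excluded for the three events and not replaced, and m others with only milder complications.

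- True rate: (m + s)/N
- Reported rate: m/(N − s)
- Shortfall: s(N − m − s)/(N(N − s))

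With s = 4 and m = 6, the true rate is 10/63 = 15.9% and the reported rate is 6/59 = 10.2%. The shortfall is 4 × 53/(63 × 59) = 5.7 percentage points.

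| s | m = 0 | m = 6 | m = 12 |
|---|---|---|---|
| 1 | 1.6 | 1.4 | 1.3 |
| 4 | 6.3 | 5.7 | 5.1 |
| 6 | 9.5 | 8.5 | 7.5 |

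(Shortfall in percentage points.) It is above zero for every s of 1 or more unless all 63 have a complication, and it depends mainly on s.

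**4. What keeping these patients could cost in power.** SAP inputs: LDH means 1406.5 and 1210 (difference 196.5), SDs 70 (POGD) and 343 (non-POGD), alpha 0.05. Group sizes: 0.38 × 63 = 23.9, so 24 v 39. Welch t-test, noncentral t, with standard error √(SD²/24 + 343²/39). Means are held fixed and only the POGD-group SD is widened. Both sidedness options are shown because the SAP says one-sided, whereas its base of 45 reproduces only two-sided at a 38% split (17 + 28, power 0.81). One-sided needs 35.

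| POGD-group SD | One-sided power | Two-sided power |
|---|---|---|
| 70 | 0.96 | 0.92 |
| 200 | 0.88 | 0.81 |
| 205 | 0.88 | 0.80 |
| 250 | 0.83 | 0.73 |
| 272 | 0.80 | 0.70 |
| 343 | 0.70 | 0.58 |

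**5. What unassessable I-FEED could cost.** With P assessed POGD patients, Q assessed non-POGD patients and u unassessed, at a fixed cutoff, counting the u all one way moves sensitivity by at most u/(P + u) and specificity by at most u/(Q + u). For u = 1 (P = 24, Q = 38) these bounds are 4.0 and 2.6 points. For u = 3 (P = 23, Q = 37) they are 11.5 and 7.5 points.

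**The case against.** The strongest defence is that the sponsor wants POGD that is not secondary to a complication. Protocol section 1 attributes POGD to the inflammatory response to surgery and favours drain fluid as less affected by unrelated infection. Excluding fistula and serious infection fits that aim, and keeping those patients lets the marker score partly by detecting leaks. This stands as an argument about which prediction analysis should be primary: the documents do not settle it, and the sponsor may justify either. It does not rescue endpoint (d) or the complication model, and the protocol nowhere states the aim.

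It is also fair that the timing evidence is thin. Fistula timing is inferred, and infection and ICU admission are not timed at all. Other criteria, such as withdrawal, postoperative intraperitoneal chemotherapy, two-stage anastomosis and pathological confirmation, can also be settled after day 1. Limiting three criteria therefore does not make the set fully identifiable on day 1, which is why all removals after sampling need reporting.

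Two stronger readings are tempting. A reader might infer that the exclusions inflate the AUC. The documents give neither marker values nor POGD status for patients with these events, so no direction follows. A reader might also infer that the gap between 59 and 63 is too small to absorb the exclusions. The SAP does not define its 5% dropout, and patients failing section 7.2 may be treated as ineligible and not as dropouts, so that argument is not supported. The harm is selection, not lost power: with 20% of 59 removed, LDH power on the SAP's inputs is still 0.90 one-sided (0.83 two-sided).

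**Conclusion.** The point holds in two parts of unequal strength.

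- **Endpoint (d) and the complication model: high confidence.** Followed as written, section 7.2 removes events that these analyses exist to count. The direction is certain whenever such a patient is excluded and at least one patient is free of complications. Over the assumed counts in the table, the shortfall runs from 1.3 to 9.5 percentage points. The size rests entirely on those assumptions.
- **Day-1 prediction: moderate confidence.** The wording permits selection on events after the sample, and nothing in the available text prevents it. Whether it occurs depends on how the criteria are applied. No bias in AUC, sensitivity or specificity is claimed in either direction.

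This should be corrected. Sections 3 and 7.2 of the Protocol and section 5 of the SAP cannot all be followed as they stand. Replacing excluded patients would restore the number but not remove the selection.

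**What to change.** Amend Protocol section 7.2 and SAP section 5 as follows.

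1. Count endpoint (d), and fit the complication model, in all consented patients who had the operation and meet the preoperative and intraoperative criteria. Include those with fistula, serious infection or ICU admission at any time after surgery.
2. For day-1 prediction of POGD, apply these three exclusions only to events known by the day-1 sample; for day-3 prediction, only to events known by the day-3 sample.
3. Prespecify a parallel analysis without patients who had later events, labelled POGD not secondary to a complication. Report both, and have the sponsor state which is primary before outcomes are analysed.
4. Define serious in advance. Report all removals after sampling, including withdrawals, by reason and day.
5. Where I-FEED cannot be assessed after such an event, report the number and show AUC, sensitivity and specificity with those patients counted all as POGD and then all as non-POGD.

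**Cost.** Wording, one definition, one parallel analysis and one table; no extra drain samples. Retained patients need I-FEED assessment and outcome data to day 30. Endpoint (d) already requires the latter, although the follow-up table in Protocol section 5 lists clinical assessments only to POD5. The downside is that POGD secondary to a complication enters one analysis and may widen the LDH SD. With the SAP means fixed and 24 v 39 patients, power falls to 0.80 at a POGD-group SD of about 272 one-sided or about 205 two-sided, against the planned 70. Those limits use all 63 patients with no dropout, and retained patients could also shift the means.
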